4.1 Inclusion Criteria

Subjects aged 18 to 70 will be **eligible for inclusion** in this study if all the following criteria apply:

1. Willing to provide written informed consent
2. Have symptoms of urinary incontinence for at least 3 consecutive months
3. For male subjects: If subject has undergone any prostate procedure, this must have occurred at least 6 months prior to screening
4. Have at least 7 incontinence episodes per week in the diary entries for the Screening Placebo Run-In Period
5. Subject is ambulatory and able to use the toilet independently
6. If subjects use pelvic floor exercises, subjects must have been on a stable exercise and activity regime for at least 3 months prior to screening and that regime must remain stable during the treatment period
7. Subject has a body mass index (BMI) $\geq 19 \text{ kg/m}^2$ but $\leq 35 \text{ kg/m}^2$ (BMI=weight [kg] / height [m^2])
8. Subjects must have a pre-dose mean systolic/diastolic blood pressure of $\leq 140/90 \text{ mmHg}$ before randomization can occur
9. For female subjects: Must not be pregnant, lactating, or actively trying to become pregnant. Subjects who are premenopausal and of childbearing potential must have a negative pregnancy test at Screening (serum) and at Day 0 (urine) and must use a medically acceptable and effective method of birth control for the duration of the study, which can include:
 - a. Having a male partner who is sterile prior to the female subject's entry into the study and is the sole sexual partner for that female subject
 - b. Use of double-barrier methods of contraception; condoms with the use of caps (with spermicide) and intra-uterine devices are acceptable
 - c. Use of hormonal contraceptives (oral, depots, patches, etc.) with double-barrier methods of contraception as outlined above

- d. True abstinence: When this is in line with the preferred and usual lifestyle of the subject (period abstinence [eg, calendar, ovulation, symptothermal, post-ovulation methods] and withdrawal are not acceptable methods of contraception)
- 10. Subjects taking oral contraceptives or hormone replacement therapy (women) or hormone adjuvant therapy (men) must have a stable dose and regimen for ≥ 3 months prior to entry into the study

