5.4 Efficacy Variables

Bladder Diary Questions

The bladder diary will be completed daily for the 7 days prior to visit 2 and visit 6, to record the number of incontinence episodes and whether these were nocturia events. If a subject has multiple events in 1 day, each event will preferably be entered separately. The number of incontinence pads used will also be recorded in the diary.

Percentage change in number of incontinence episodes in a week

The number of incontinence episodes entered into the eCRF is the total number of events a subject recorded during the 7day period prior to visit 2 and visit 6. This number will be directly used in the calculation of % change in number of incontinence episodes in a week

Number of Incontinence Episodes/24 hours (daily average)

The number of incontinence episodes entered in the eCRF will be divided by 7 to compute the number of episodes/24 hours (daily average). This consideration follows the assumption that the bladder diary will be filled by the subject for the 7 days prior to Visit 2 and Visit 6 and that the patient entered all episodes occurred in this period. Therefore, the following formula will be used:

$$\text{Number of Incontinence episodes / 24 hours} = \frac{\text{Number of incontinence episodes recorded}}{7}$$

Number of Nocturia Episodes in a week

The number of nocturia episodes entered in the eCRF is the total number of nocturia episodes a subject recorded during the 7day period prior to Visit 2 and Visit 6. The value entered in the eCRF will be used in the efficacy analysis of nocturia episodes without any adjustment.

Number of Incontinence Pads per week

The number of incontinence pads entered in the diary represents the number of pads used in a week, therefore the value entered in the eCRF will be used in the analysis without any adjustment.

This consideration follows the assumption that the bladder diary is completed by the subject for the 7 days prior to Visit 2 and Visit 6 and that the patient entered all pads used in this period.

Proportion of subjects who become continent

A subject is defined as continent if he/she has no incontinence episodes.

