6.9 Efficacy Analyses

Efficacy will be assessed by the number of urinary incontinence episodes. There is only one hypothesis so there will be no adjustment for multiplicity.

The efficacy analysis will be performed on the ITT and PP populations.

There will not be an adjustment for multiple comparisons for these efficacy analyses.

Baseline for all efficacy endpoints will be defined as the last week of the Screening Placebo Run-In Period (Visit 2). The final measurement (endpoint) will be defined as Week 8 (Visit 6).

1. Percentage change from end of the Screening Placebo Run-In Period to Week 8 in the number of incontinence episodes in a week

The efficacy analysis planned is an analysis of covariance model (ANCOVA). Percentage change in the number incontinence episodes/week is the response variable. The factor variables will be dose and centre. If the center effect is significant, summary statistics will be presented to describe the effect. The covariate will be end of the Screening Placebo Run-In Period episodes of incontinence.

The percentage change, $\%UIE_i$, for subjects in each arm, is expressed as the ratio of the total number of urinary incontinence episodes in a week between final measurement ($UIE_{i,end}$) and baseline ($UIE_{i,base}$)

$$\%UIE_i = \frac{UIE_{i,end}}{UIE_{i,base}}$$

Since percentage change from baseline does not have the properties of additivity and symmetry, it will be log-transformed, and the response variable will be the natural logarithm of the ratio of Week 8 (Visit 6) to Baseline, as shown below:

$$\log(\%UIE_i) = \log\left(\frac{UIE_{i,end}}{UIE_{i,base}}\right)$$

The hypothesis test being conducted is as follows:

$$\begin{aligned} H_0: \log(\%UIE_{\text{Litoxetine}}) - \log(\%UIE_{\text{Placebo}}) &= 0 \\ H_1: \log(\%UIE_{\text{Litoxetine}}) - \log(\%UIE_{\text{Placebo}}) &\neq 0, \end{aligned}$$

This is equivalent to testing the hypothesis:

$$H_0: \log\left(\frac{\%UIE_{Litoxetine}}{\%UIE_{Placebo}}\right) = 0$$

The result of the ANCOVA model will be expressed as log % and then back transformed to percentage change. Therefore, H_0 can be interpreted as:

$$H_0: \frac{\%UIE_{Litoxetine}}{\%UIE_{Placebo}} = 1$$

This makes the actual statistics:

$$\delta = \log(\%UIE_{Litoxetine}) - \log(\%UIE_{Placebo}) = \log\left(\frac{\%UIE_{Litoxetine}}{\%UIE_{Placebo}}\right)$$

When back-transformed, this is expressed as follows:

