$$\Delta = \exp\left(\log\left(\frac{\%UIE_{Litoxetine}}{\%UIE_{Placebo}}\right)\right) = \frac{\%UIE_{Litoxetine}}{\%UIE_{Placebo}}$$

$\%UIE_i$ is the ratio of the total number of urinary incontinence episodes in a week at endpoint (Visit 6) ($UIE_{i,end}$) to the total number of urinary incontinence episodes in a week at baseline ($UIE_{i,base}$) for arm i , with i equal to Litoxetine or Placebo.

An ANCOVA will be performed to compare δ to 0; the test will provide an appropriate p-value with a significance level alpha equal to 0.05. This p-value will be computing the probability of observing a difference among arms.

Numbers of incontinence episodes equal to 0 (not missing) will be imputed as 0.4 to allow for the log transformation.

2. Absolute change from end of the Screening Placebo Run-In Period to Week 8 in the number of incontinence episodes/24 hours (daily average)

The analysis planned is an analysis of covariance model (ANCOVA). Absolute change in the total number of incontinence episodes/24 hours is the response variable. The factor variables will be dose and centre. The covariate will be end of the Screening Placebo Run-In Period episodes of incontinence.

Number of incontinence episodes/24 hours will be computed as Total Number of incontinence episodes recorded during the 7-day period and entered in the eCRF divided by 7, as defined in Section 5.4.

The hypothesis test being conducted is as follows:

$$H_0: \Delta UIE_{Litoxetine} - \Delta UIE_{Placebo} = 0$$
$$H_1: \Delta UIE_{Litoxetine} - \Delta UIE_{Placebo} \neq 0$$

Where ΔUIE_i is the absolute change, for subjects in arm i , in the number of incontinence episodes/24 hours as defined above from baseline ($UIE_{i,base}$) to the final measurement ($UIE_{i,end}$):

$$\Delta UIE_i = UIE_{i,end} - UIE_{i,base}.$$

Where i goes from 1 to 2 and it represents the 2 arms: Litoxetine and Placebo.

3. Proportion of subjects who become continent at Week 8

A subject is defined as continent if s/he has no incontinence episodes at Visit 6 (Week 8). Frequencies will be used to describe the proportion of subjects who are continent at Week 8. The proportion will be computed on the total number of subjects for each arm at baseline. The category Missing will be included in the analysis, to consider subjects who do not attend the visit or who have missing values for that visit.

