The change in the total number of incontinence episodes/24 hours will be analysed with an ANCOVA model. It will follow the efficacy analysis described in section 6.9 point 2. In the litoxetine group, only patients who did not have a dose reduction will be considered. Therefore, subjects who took the 30 mg dose at visit 6 will be considered in the litoxetine group.

5. Percentage change from end of the Screening Placebo Run-In Period to Week 8 (Visit 6) in the number of incontinence episodes/24 hours (daily average)

This exploratory analysis will use an ANCOVA model. It will follow the efficacy analysis described in section 6.9 point 1.

The number of incontinence episodes/24 hours (daily average) will be used as endpoint.

6. Change from end of the Screening Placebo Run-In Period to Week 8 (Visit 6) in the number of incontinence episodes in a week

The change in incontinence episodes in a week will be analysed with an ANCOVA model. It will follow the efficacy analysis described in section 6.9 point 2.

The total number of incontinence episodes in a week will be used as endpoint.

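### SAP 6.9.1 point 5 carries the 0.4 substitute for zero over to the daily scale unchanged; read as written, continent subjects then score worse than subjects with 1 or 2 episodes a week at the same baseline

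*SAP*

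**What the plan says.** SAP 6.9 point 1 defines the first efficacy analysis: "Percentage change in the number incontinence episodes/week is the response variable". The response is log-transformed as the ratio of Visit 6 to baseline, and the section ends with a rule for zeros: "Numbers of incontinence episodes equal to 0 (not missing) will be imputed as 0.4 to allow for the log transformation". No unit is attached to the 0.4.

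SAP 6.9.1 point 5 reuses this method: "This exploratory analysis will use an ANCOVA model. It will follow the efficacy analysis described in section 6.9 point 1". It changes only the variable: "The number of incontinence episodes/24 hours (daily average) will be used as endpoint". SAP 5.4 derives the daily average by dividing the eCRF count by 7, so a continent subject's daily value is 0. Neither section says whether the substitution comes before or after that division.

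SAP 6.9.1 point 6 does the reverse for absolute change. In 6.9 point 2, "Absolute change in the total number of incontinence episodes/24 hours is the response variable"; in 6.9.1 point 6, "The total number of incontinence episodes in a week will be used as endpoint", with the same ANCOVA.

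Protocol 4.1 sets the lowest eligible baseline: "Have at least 7 incontinence episodes per week in the diary entries for the Screening Placebo Run-In Period". Protocol 8.8.1 lists percentage change in episodes per 24 hours first among the efficacy endpoints. SAP 1.5 moved that endpoint to the weekly count, which leaves 6.9.1 point 5 as the only planned table on the protocol's first-listed efficacy scale.

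**The concern.** A substitute for zero should lie between zero and the smallest positive value that can be observed. On the weekly count that value is 1, so 0.4 keeps the order. On the daily average it is 1/7, so 0.4 lies above it.

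Eligible subjects start at 7 or more episodes per week, so among them zeros arise only at Visit 6, in subjects who meet the SAP's own definition of continence. These are the best responders, and they are the subjects the rule would mis-rank. They would count as full successes in 6.9 point 3 and as less than the best in 6.9.1 point 5. If the daily and weekly percentage-change tables then differed, a reader could take the gap as fragility of the weekly result when it is only a matter of scale.

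**Working it through.** **Inputs.** Substitute for zero: 0.4 (SAP 6.9 point 1). Daily value = weekly count / 7 (SAP 5.4). Response = ln(Visit 6 / baseline) (SAP 6.9 point 1). Minimum baseline: 7 per week (Protocol 4.1). The 0.4 is a chosen constant, so there is no plan figure to reproduce.

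**Step 1: the constant on each scale.** 0.4 per day × 7 = 2.8 per week. Counts of 1, 2 and 3 per week are 1/7 = 0.143, 2/7 = 0.286 and 3/7 = 0.429 per day. So 0.4 per day lies between 2 and 3 episodes per week.

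**Step 2: percentage reduction at equal baseline.** For baseline b per week, a subject with k episodes scores 1 − k/b. A continent subject scores 1 − 0.4/b on the weekly scale and 1 − 0.4/(b/7) = 1 − 2.8/b on the daily scale as written.

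| Baseline per week | Continent, weekly analysis | Continent, 0.4 per day | 1 per week | 2 per week | 3 per week |
|---|---|---|---|---|---|
| 7 | 94.3% | 60.0% | 85.7% | 71.4% | 57.1% |
| 14 | 97.1% | 80.0% | 92.9% | 85.7% | 78.6% |
| 21 | 98.1% | 86.7% | 95.2% | 90.5% | 85.7% |
| 28 | 98.6% | 90.0% | 96.4% | 92.9% | 89.3% |

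At every baseline the continent subject falls below 1 and 2 per week and just above 3 per week.

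**Step 3: shift per continent subject.** ln(2.8/b) − ln(0.4/b) = ln 7 = 1.946, whatever the baseline. Subjects without a zero have identical ratios on both scales, because the 7s cancel.

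**Step 4: effect on the treatment comparison.** Before covariate adjustment, the log difference between arms moves by ln 7 × (continent proportion on litoxetine − continent proportion on placebo), so the back-transformed ratio is multiplied by 7 to the power of that difference. The documents give no continence rates. Assumed differences of 5, 10 and 15 percentage points in favour of litoxetine give factors of 7^0.05 = 1.10, 7^0.10 = 1.21 and 7^0.15 = 1.34. A difference in favour of placebo moves the ratio the other way, and with no difference there is no mean shift.

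A simulation gives the same picture. It used 1,000 data sets, 52:26 allocation, assumed continence of 25% against 10%, and ANCOVA with site and baseline. The mean ratio was 0.55 on the weekly scale and 0.74 with 0.4 per day. The share significant at 0.05 was 40% and 27%. This illustrates the mechanism and does not forecast the trial.

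**Step 5: substitution before division.** 0.4/7 = 0.057 per day, below 0.143, so the order 0 < 1 < 2 returns. In one simulated data set the weekly analysis and this version both gave a log ratio of −0.461, p = 0.193. With 0.4 per day the same data gave −0.136, p = 0.569.

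**Step 6: point 6.** Weekly absolute change is 7 times daily absolute change. In the same simulated data set the estimates were −0.0849 per day and −0.5943 per week (−0.0849 × 7 = −0.5943), both with p = 0.8151, whichever scale the baseline covariate was on. Multiple imputation does not alter this, because SAP 6.1 imputes the weekly total.

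**The case against.** The strongest reply is that the SAP never says 0.4 per day. The zero rule speaks of numbers of episodes, and SAP 5.4 uses that term for the 7-day total in the eCRF, with the daily average as a separate, derived variable. A programmer could fairly put 0.4 on the recorded count and divide afterwards, and no mis-ranking would occur. This stands as a possible reading. The plainer one is that point 5 takes the daily average as its endpoint and applies the 6.9 point 1 method, zero rule included, at the log step. The result should not depend on an unrecorded programming choice.

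Four stronger inferences are tempting, and the documents do not support them:

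- **Continent subjects always rank worse.** This holds only at equal baseline. A continent subject with baseline 28 per week scores 0.4/4 = 0.10, better than 1/7 = 0.143 for a subject with 1 per week from a baseline of 7.
- **Point 5 would contradict the weekly result.** No continence rate is given. The illustration shows attenuation, and with few continent subjects the gap may be small.
- **Point 6 is an error.** It is a harmless unit conversion of 6.9 point 2. It does not duplicate the first-listed percentage-change analysis.
- **Points 5 and 6 must be deleted.** SAP 6.9.1 introduces them as a third set of tables and calls point 5 exploratory. They can be read as reporting each endpoint in the other unit, although the SAP does not state that purpose. Deleting point 5 would remove the only table on the protocol's first-listed scale. The checks on imputation and dose reduction sit in points 1 to 4.

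**Conclusion.** The concern holds for SAP 6.9.1 point 5 read as written. The zero rule is carried to a scale seven times smaller without rescaling, so at the same baseline a continent subject scores worse than one with 1 or 2 episodes per week. The per-subject shift of 1.95 log units is exact. The size and direction of the effect on the treatment comparison are unknown without continence rates.

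On neither reading does point 5 test robustness: it is either distorted by the constant or identical to 6.9 point 1. Point 6 cannot differ from 6.9 point 2 in its p-value; its estimate and confidence interval are simply multiplied by 7. If points 5 and 6 are run without imputation, the same relations hold against the unimputed versions.

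The reach is limited. Efficacy is secondary and exploratory here. The weekly percentage-change analysis, where 0.4 lies below 1, and the primary safety analyses are not affected. The correction is still worth making, because it costs one sentence.

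**What to change.** 1. In SAP 6.9.1 point 5, state that zeros are replaced by 0.4 on the weekly eCRF count before division by 7 (0.057 per day). In 6.9 point 1, add that the 0.4 is in episodes per week.
2. Label points 5 and 6 as unit conversions of 6.9 points 1 and 2, and say that point 5 must reproduce the ratio and p-value of 6.9 point 1, and point 6 the p-value of 6.9 point 2. Any mismatch then signals a programming error.
3. Optionally, add a real check of the zero rule: repeat 6.9 point 1 with weekly constants of 0.5 and 1, or on ranks.

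Items 1 and 2 change SAP wording only. Item 3 adds a few model runs. None needs new data.

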6.9.2 Exploratory Efficacy Analyses

The severity of incontinence episodes will be explored dividing the population in subjects with less/more severe UI. Less severe is defined as the population who has incontinence episode frequency below the study median at baseline, while more severe is defined as the population who has incontinence episode frequency above the study median at baseline.

Based on the assessment of the variability of the data and the size of each subgroup, the efficacy analysis will be performed on the subgroups.

Baseline severity threshold is defined as the median value of incontinence episodes at baseline.

These analyses will be performed on the PP population only.

1. Percentage change from end of the Screening Placebo Run-In Period to Week 8 (Visit 6) in the number of incontinence episodes in a week as a function of degree of incontinence

The percentage change in the total number of incontinence episodes in a week will be analysed with an ANCOVA model. It will follow the efficacy analysis described in section 6.9 point 1. Patients will be divided in two groups depending on the baseline severity of incontinence episodes.

The median number of incontinence episodes at baseline will be computed on the randomised population. Two analyses will be performed, one on subjects whose baseline number of incontinence episodes is less than the median, and the other on subjects whose baseline number of incontinence episodes is greater than or equal to the median.

2. Change from end of the Screening Placebo Run-In Period to Week 8 (Visit 6) in the number of incontinence episodes/24 hours (daily average) as a function of degree of incontinence.

The change in the number of incontinence episodes/24 hours (daily average) will be analysed with an ANCOVA model. It will follow the efficacy analysis described in section 6.9 point 2. Patients will be divided in two groups depending on the baseline severity of incontinence episodes.

The median number of incontinence episodes at baseline will be computed on the randomised population. Two analyses will be performed, one on subjects whose baseline number of incontinence episodes is less than the median, and the other on subjects whose baseline number of incontinence episodes is greater than or equal to the median.

7. General Considerations

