8.8 Efficacy Endpoints and Analyses

8.8.1 *Efficacy Endpoints*

Baseline for all efficacy endpoints will be defined as the last week of the Screening Placebo Run-In Period.

- Percentage change from the end of the Screening Placebo Run-In Period to Week 8 in the number of incontinence episodes/24 hours
- Absolute change from the end of the Screening Placebo Run-In Period to Week 8 in the number of incontinence episodes/24 hours

Number of incontinence episodes/24 hours will be computed as Total Number of incontinence episodes recorded over the 7 days/7.

- Proportion of subjects who become continent at Week 8
- Change from end of the Screening Placebo Run-In Period to Week 8 in the number of incontinence pads used per week

8.8.2 *Efficacy Analyses*

The efficacy analysis will be performed on the ITT, mITT, and PP populations. The efficacy analysis will be performed on the ITT population, with the analysis on the mITT and PP populations as part of secondary efficacy analysis.

The efficacy analysis planned is a mixed effects model with repeated measures (MMRM). Percent reduction in incontinence episodes as the response variable is the first efficacy endpoint. The factor variable will be dose and the covariate will be baseline episodes (end of placebo run

in) of incontinence. Visits within subjects will provide the random effects of the mixed model. There is only one hypothesis so there will be no adjustment for multiplicity. Further efficacy analysis will be conducted similarly, with appropriate baseline measure. There will not be an adjustment for multiple comparisons for these secondary analyses.

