2.4 Secondary Endpoints(s)

Efficacy:

1. Percentage change from end of the Screening Placebo Run-In Period to Week 8 (Visit 6) in the number of incontinence episodes in a week
2. Absolute change from end of the Screening Placebo Run-In Period to Week 8 (Visit 6) in the number of incontinence episodes/24 hours (daily average)
3. Proportion of subjects who become continent at Week 8 (Visit 6)
4. Change from end of the Screening Placebo Run-In Period to Week 8 (Visit 6) in the total number of incontinence pads used per week
5. Percentage change from end of the Screening Placebo Run-In Period to Week 8 (Visit 6) in the number of nocturia episodes in a week.

3. Study Design

This is a Phase 1/2a, double-blind, randomised, placebo-controlled, parallel-group study in subjects 18 to 70 years old diagnosed with UI.

The study will include a 2-week, single-blind (subject blind) Screening Placebo Run-In Period and an 8-week double-blind Treatment Period. The Treatment Period will be followed by a 1 week Dose-tapering Period and subjects will return to the clinic for a safety Follow up Visit 4 weeks after treatment is completed. This provides a total study duration of 15 weeks. No interim analysis is planned.

All subjects will enter the Screening Placebo Run-In Period during which eligibility will be assessed and single blind placebo run-in medication will be provided. In the latter half of this period, the subject will complete 7 days of bladder diary to capture incontinence events and pad usage. Subjects who continue to meet eligibility criteria after the Screening Placebo Run-In period, will enter the Treatment Period and be randomly assigned (2:1) to receive study drug (litoxetine10 mg, 20 mg, 30mg) or matching placebo BID.

Litoxetine or placebo treatment will be provided with dose titration, starting with 10 mg BID for 1 week, escalated to 20 mg BID for 1 week, and subsequently escalated to 30 mg BID for 6 weeks' duration (for a total treatment period of 8 weeks).

If the subject does not tolerate the last dose level escalation (i.e. cannot tolerate 30 mg BID), the dose can be reduced to the previous dose level (20 mg BID). If the patient does not tolerate the lower dose level (20 mg BID) s/he will be discontinued from the study. After 8 weeks of treatment, doses will be reduced by 50% over 1 week to taper off treatment. A safety follow up visit will occur 4 weeks after treatment is permanently stopped (total study duration 15 weeks).

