4.1 Study Populations

The study population will consist of subjects with UI. Subjects must be able to provide written consent and meet all the inclusion criteria and none of the exclusion criteria.

A valid efficacy measurement is defined as a valid number of incontinence episodes as recorded in the bladder diary and uploaded in the eCRF at Visit 2 and Visit 6, i.e. either as 0 or greater than 0.

There are 4 analysis populations for this study:

Randomised population:

Defined as all subjects randomised to treatment (Visit 2).

Safety population:

Defined as all subjects who are randomised to treatment (Visit 2), receive study drug, and undergo at least 1 visit.

Intent-to-Treat (ITT) population:

Defined as all subjects who are randomized to treatment (Visit 2), receive at least one dose of study drug and have a valid efficacy measurement at Baseline (Visit 2).

Per Protocol (PP) population:

Defined as those subjects who are randomised, receive at least one dose of study drug, provide a valid efficacy measurement at Baseline (Visit 2) and a valid end of study primary efficacy endpoint (Visit 6), and have completed the study without a major protocol deviation.

The following populations are defined for analysis purposes:

1. Enrolled Population: each subject that signed the Informed Consent form and entered the Screening Period.
2. Completers Population: each subject that completed the trial, per protocol.
3. Full Analysis Set Population: each subject which is in either ITT or PP population.

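### The two exploratory baseline-severity analyses are run on the Per Protocol set alone, so they exclude subjects for post-randomisation reasons and have no ITT counterpart

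*SAP*

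**What the plan says.** - **Severity analyses.** SAP 6.9.2 analyses percentage change in weekly episodes and absolute change in episodes per 24 hours, separately below and at or above the baseline median. It says: "These analyses will be performed on the PP population only". The cut-point comes from a wider set: "The median number of incontinence episodes at baseline will be computed on the randomised population".
- **PP definition.** SAP 4.1 requires randomisation, at least one dose, valid counts at Visits 2 and 6, and that subjects "have completed the study without a major protocol deviation".
- **Main efficacy analyses.** SAP 6.9: "The efficacy analysis will be performed on the ITT and PP populations". SAP 6.3 adds that the ITT analysis of episodes uses both valid and imputed Visit 6 values. SAP 6.9.1 runs its sensitivity analyses on ITT only and explains why.
- **Protocol 8.8.2.** "The efficacy analysis will be performed on the ITT population, with the analysis on the mITT and PP populations" are to be analysed, the latter two as part of the secondary efficacy analysis.
- **Discontinuation.** SAP section 3, on subjects whose dose has been reduced: "If the patient does not tolerate the lower dose level (20 mg BID) s/he will be discontinued from the study".
- **Early leavers.** Note 4 to the SAP schedule of assessments requires all Visit 6 procedures for subjects withdrawn prematurely. Bladder-diary review and collection is one of those procedures.

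**The concern.** The severity analyses are the only efficacy analyses in the SAP without an ITT result. SAP 1.5 drops the protocol's mITT set on the ground that ITT and PP together describe the data adequately. Here only one of the two is used.

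PP membership is decided after randomisation. Stopping early, intolerance of treatment and major deviations can each depend on the treatment received. Within a severity half, the litoxetine and placebo subjects who remain need not be comparable, and retention could differ between the halves. A difference in effect by severity might then partly reflect who stayed, and a real difference might be masked. With PP alone, a reader has nothing to check the result against.

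PP also discards outcomes that were measured. A completer with a major deviation may have a Visit 6 diary, and an early leaver may supply one at the early-termination visit. PP excludes both.

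**Working it through.** **Inputs.** 78 randomised, 30% post-randomisation dropout and 60 evaluable (SAP 3.1; protocol 8.10). Allocation 2:1 (SAP 3.2), so about 52 litoxetine and 26 placebo. Up to 15 sites (protocol synopsis), with centre as a model factor (SAP 6.9).

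**Step 1: the plan's own figure.** 78 × (1 − 0.30) = 54.6, not 60. The stated pair arises from 60 × 1.3 = 78. The loss implied by 60 of 78 is 1 − 60/78 = 23.1%. The inconsistency is a separate matter, so both rates are carried forward.

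**Step 2: subjects lost to PP through dropout alone.** At 30%: 78 × 0.30 = 23.4. At the implied rate: 78 − 60 = 18.

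**Step 3: size of each severity half.** I assume an even median split and 2:1 allocation within each half. The 95% half-width for the difference between arms, in SD units, is 1.96 × √(1/n_L + 1/n_P). Residual degrees of freedom are n − 17 (intercept, treatment, baseline and 14 centre terms), if all 15 sites appear in each half.

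| Set | Per half | Litoxetine / placebo | Half-width (SD) | Residual df |
|---|---|---|---|---|
| All randomised | 78/2 = 39 | 26 / 13 | 0.67 | 22 |
| PP, 23% loss | 60/2 = 30 | 20 / 10 | 0.76 | 13 |
| PP, 30% loss | 54.6/2 = 27.3 | 18.2 / 9.1 | 0.80 | about 10 |

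The PP rows are upper limits on size, because completers with a major deviation are also removed. The first row is a ceiling for ITT: SAP 4.1 requires a dose and a valid baseline, and imputed values do not carry the information of observed ones.

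**Step 4: how uneven the loss could be.** The documents do not split dropout by arm, so this is a range of assumptions. Loss per arm is leavers × share ÷ arm size.

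| Share of leavers on litoxetine | 23.4 leavers: litoxetine / placebo loss | 18 leavers: litoxetine / placebo loss |
|---|---|---|
| 2/3 (proportional) | 30% / 30% | 23% / 23% |
| 80% | 36% / 18% | 28% / 14% |
| All | 45% / 0% | 35% / 0% |

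The retained arms could be equally depleted or very unequally depleted, and nothing in the plan says which.

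**The case against.** **Low stakes.** Safety is the primary objective. Efficacy is exploratory, and SAP 6.9.2 is an exploratory subgroup analysis within it, to be run subject to data variability and subgroup size. The severity split is not in the protocol, so protocol 8.8.2 is not contradicted. All of this stands. It limits the weight of the point but supplies no reason for omitting ITT.

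**ITT may not cure the selection.** Efficacy is measured only at Visits 2 and 6, so a leaver without a diary has no post-baseline efficacy data. The SAP 6.1 imputation assumes missing at random. If treatment is in the imputation model, the imputed result would roughly reproduce the effect in subjects with observed values. If it is not, any shrinkage comes from the imputation. SAP 6.1 does not list the covariates. This objection largely stands. What survives is that ITT uses observed Visit 6 values that PP throws away.

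**The selection is narrower than it looks.** Subjects reduced to 20 mg BID who complete can remain in PP, so it is not simply a set of subjects who tolerated full titration. A Visit 6 timing deviation is major only at 8 or more days outside the window (SAP 4.3). Medication deviations are reviewed blind and can lead to exclusion from ITT as well as PP. Taking the cut-point from all randomised subjects does no harm, since baseline precedes treatment. These points stand.

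**A stronger reading.** A reader might infer that PP overstates benefit by a known amount. If a fraction d of litoxetine subjects leave and keep a share k of the benefit, the ratio of the completer effect to the all-randomised effect is 1/[(1 − d) + dk]. With d = 0.30 this gives 1/0.70 = 1.43 for k = 0 and 1/0.85 = 1.18 for k = 0.5. The documents support neither value of k, nor the accompanying assumption that placebo leavers resemble placebo completers. If placebo subjects left for lack of effect, PP would understate benefit. If dropout and retained benefit were the same in both halves, both effects would scale alike and no severity difference would be created where none existed. These figures are illustrations under an assumption, not estimates for this trial.

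**Conclusion.** The point holds as a minor one. SAP 6.9.2 confines the severity analyses to a set formed after randomisation and provides no ITT result, unlike SAP 6.9. Dropout alone would remove 18 to about 23 of 78 subjects. At most about 27 to 30 would remain per half rather than 39, assuming an even split. The direction and size of any bias cannot be derived, because dropout by arm, reason and severity is not given. An overstated benefit is possible but not shown. The main ITT and PP efficacy results and the safety analyses are unaffected.

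**What to change.** In SAP 6.9.2, replace the PP restriction with text to this effect: *both severity analyses will be performed on the ITT population (section 4.1) as the main severity result, using all observed Visit 6 or early-termination diary values and the section 6.1 imputation for those still missing; the same analyses on the PP population will be supportive.* Saying explicitly that an early-termination diary counts as an observed endpoint matters, because that is where ITT gains real data over PP.

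The cost is one sentence and one more set of tables, with no new data collection. The downside is that, for leavers with no diary, the ITT result depends on the missing-at-random imputation. The change therefore reduces the selection problem but does not remove it, and the PP tables remain useful alongside.
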